10.2.1 Early stopping criteria

An early stopping criterion for toxicity for the whole trial itself would be if ≥ 2 of the first 9 or ≥ 4 of the first 17 patients has unacceptable toxicity or an irAE that required discontinuation of avelumab and/or initiation corticosteroid treatment.

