The standard immune related adverse event (irAE) treatment decision algorithm [66] will be followed to address avelumab related AEs and any patient who requires corticosteroid treatment for irAE will discontinue their rhIL-15 treatment. Since the expected frequency of grade 3 or 4 irAEs with single agent avelumab is extremely low (< 1%), irAE requiring corticosteroid treatment during the first cycle of treatment for the run-in cohort of patients will also be considered a DLT. All patients in the run-in cohort (Cohort 1) must complete their first 28-day cycle of treatment without experiencing a DLT before enrollment into the 4 mcg/kg cohort is initiated.

The efficacy of the combination will be assessed in a Simon two-stage phase II clinical trial scheme that treats a total of minimum 9 or maximum 17 patients at the 4 mcg/kg dose level depending on demonstration of clinical activity in the initial group of patients.

See Section **10.2.1** for details regarding early stopping criteria for the whole trial.

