10.2 SAMPLE SIZE DETERMINATION

The primary objective of this trial is to determine the efficacy of combination treatment of CIV rhIL-15 on days 1-5 and IV anti PDL-1 avelumab on day 8 and 22 of the 28-day cycle in patients with treatment refractory PD-L1+ ($\geq 5\%$) metastatic clear-cell renal carcinoma in terms of overall response. All patients must have failed or relapsed and have progressive disease after at least 2 prior therapies that include multityrosine kinase inhibitor like axitinib or sunitinib and an anti-PD1

or PD-L1 ICI therapy like nivolumab. The primary endpoint will be overall response (OR) per irRECIST 1.1 criteria.

A Simon two stage Simon Optimal Design will be used for the analysis of the primary endpoint of overall response rate. A minimum of 12 (3 in the 2mcg/kg safety run-in cohort (Cohort 1) and 9 evaluable in the first stage) and maximum of 25 patients will be enrolled in order to have 17 evaluable patients treated at the recommended phase 2 dose for the CIV rhIL-15 schedule at dose 4 mcg/kg/day. A maximum of 19 patients may be enrolled in the phase 2 part of this trial to compensate for inevaluable patients. The sample size for this trial is based on the plan for 3 to 6 patients treated in the 2 mcg/kg/day safety run-in cohort and to accurately assess target 25% response rate in the 4 mcg/kg dosing cohort with a power of 80% to determine the feasibility if this rate were true. The overall Type I error was set at 5% and power at 80% that assumes a null hypothesis success rate of 5% versus a treatment with a 25% response rate. Patients treated in the 2 mcg/kg/day safety cohort will not be included in the primary end point analysis but will be included in the safety cohort and be assessed for the secondary endpoints.

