Stage 1 for the 4 mcg/kg dose level will consist of 9 evaluable patients to provide evidence of effectiveness and safety. If at least 1 of the 9 patients achieves a radiographic response (> 20% reduction in tumor volume) the study will be allowed to recruit the total sample size of 17 evaluable patients, otherwise it will be stopped for futility (Stage I boundary). The second stage of the design requires 3 or more of the 17 patients to have a positive response for the treatment to be considered worthy of further investigation. If the null hypothesis is true, there is a 63% chance of terminating after Stage I. If the probability of success is actually 0.25, there is a 92% chance that 1 or more patients will exhibit a 20% reduction in tumor volume at Stage I. Patients discontinued from the trial will not be replaced and counted in an "Intent to Treat" analysis as evaluable and treatment failures. At the end of the trial, we will report poor performance if the treatment is rejected at Stage I, not meeting the criteria of at least 1 success in 9 cases. If there is no success at Stage II (at most 2 responses in 17 patients), we will report a failure to reject the null hypothesis using the conditional probability of the added patients.

To ensure that this combination, which has not been administered to patients previously, and the dose levels chosen for CIV rhIL-15 are safe, 3 to 6 patients will be treated at the 2 mcg/kg/day dose level to confirm the absence of dose limiting toxicities. Once the safety of the 2 mcg/kg dose level is confirmed the first 3 or 6 patients treated at the intended phase II dose of 4 mcg/kg/day will be evaluated likewise for dose limiting toxicities. If unacceptable toxicity is observed in ≥ 2 of the first 3 or 6 patients treated at these dose levels, entry into the trial and all treatment will be halted to review the safety data to determine if the treatment plan should be altered or the study terminated. If DLT that halts the trial is not observed in these safety run-in cohorts, the trial will proceed to the efficacy assessment as specified above. The protocol will be amended to include information from the Safety Run-in cohorts prior to opening phase II.

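### The toxicity stopping rule in Section 10.2.1 does not define its first 9 and first 17 patients; read literally, 2 mcg/kg patients take places in the count and the last 4 mcg/kg patients fall outside it

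*Combined protocol and SAP*

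**What the plan says.** Section 10.2.1 reads "An early stopping criterion for toxicity for the whole trial itself would be if" at least 2 of the first 9 or at least 4 "of the first 17 patients has unacceptable toxicity or an irAE that required discontinuation of avelumab and/or initiation corticosteroid treatment". It names no dose level or cohort. Section 3.1 points to it "for details regarding early stopping criteria for the whole trial".

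On who enters and when, Section 10.2 says that "3 to 6 patients will be treated at the 2 mcg/kg/day dose level to confirm the absence of dose limiting toxicities", and these patients come before anyone is treated at 4 mcg/kg. The ceilings are a "maximum of 25 patients will be enrolled in order to have 17 evaluable patients treated at the recommended phase 2 dose", and "A maximum of 19 patients may be enrolled in the phase 2 part of this trial". The 2 mcg/kg patients are left out of the primary endpoint but kept in the safety cohort. Section 10.3.1 makes every treated patient evaluable for toxicity.

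The numbers 9 and 17 also appear as the Simon stage sizes. Section 3.1 describes a scheme that "treats a total of minimum 9 or maximum 17 patients at the 4 mcg/kg dose level", and Section 10.2 states: "Stage 1 for the 4 mcg/kg dose level will consist of 9 evaluable patients to provide evidence of effectiveness and safety".

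A separate run-in rule (Sections 3.1 and 10.2, Table 6) halts the trial if 2 or more of the first 3 or 6 patients at a dose level have a dose-limiting toxicity (DLT). Section 3.1.1 limits DLTs to the first 28 days and to the run-in cohort.

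**The concern.** The rule can be applied in two ways, and they can give different decisions on the same data. If all enrolled patients are counted, the earliest places go to patients on the lower rhIL-15 dose, so the count holds less information about the dose under test. The latest patients, all at 4 mcg/kg, are then beyond its reach.

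The run-in rule does not fill this gap. It covers only DLTs in the first 28 days, in the first 3 or 6 patients per dose level. Section 1.3 expects the immune-related events (irAEs) of most concern about 2 to 3 months after treatment starts, and the median onsets in Table 4 run from 2.1 to 3.2 months. Later irAEs, and all toxicity in patients treated after the run-in, depend on Section 10.2.1 for a numerical limit. Section 10.2 itself notes that the combination has not been given to patients before.

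**Working it through.** **Source of 9 and 17.** The Simon design (continue with at least 1 response in 9; success with at least 3 in 17) reproduces. The chance of stopping at Stage 1 under the 5% null is 0.95^9 = 0.630 (plan: 63%). The chance of continuing at 25% is 1 − 0.75^9 = 0.925 (plan: 92%). Exact type I error is 0.047 and power 0.812. The plan gives no operating characteristics for the toxicity rule, so there is no stated figure to check there.

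**Places in the count if all enrolled patients are counted.** Let k be the number treated at 2 mcg/kg (3 or 6), and let 17 or 19 patients be treated at 4 mcg/kg, including that dose's run-in patients (6 + 19 = 25, the stated ceiling).

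- 4 mcg/kg patients in the first 9: 9 − k = 6 or 3.
- 4 mcg/kg patients in the first 17: 17 − k = 14 or 11.
- 4 mcg/kg patients after the 17th place, 17 treated: 17 − 14 = 3, or 17 − 11 = 6.
- The same with 19 treated: 19 − 14 = 5, or 19 − 11 = 8.

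Under a 4 mcg/kg-only count, 19 − 17 = 2 patients at most are outside. None of this depends on an assumed event rate.

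**Stopping probabilities.** The documents give no toxicity rates for the combination, so the rate p at 4 mcg/kg is an assumption, varied from 10% to 40%. Patients are taken as independent and outcomes as known at each look. If the k earlier patients had e events, then X ~ Bin(9 − k, p) counts events at 4 mcg/kg up to the first look, and Y ~ Bin(8, p) counts those between the looks:

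- by look 1: P(X ≥ 2 − e)
- by look 2: P(X ≥ 2 − e) + Σ P(X = x)·P(Y ≥ 4 − e − x), summed over x < 2 − e

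The 4 mcg/kg-only count is k = 0, e = 0. For the whole-trial count, two paths follow the run-in rules. In the first, three patients at 2 mcg/kg have no event. In the second, six are treated, one had the DLT that triggered expansion (counted as an event) and the other five had none.

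At p = 0.30, P(Y ≥ 3) = 0.448 and P(Y ≥ 4) = 0.194:

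- 4 mcg/kg only: P(X = 0) = 0.040 and P(X = 1) = 0.156, so look 1 is 0.804. Look 2 is 0.804 + 0.040·0.194 + 0.156·0.448 = 0.882.
- Three event-free: P(X = 0) = 0.118 and P(X = 1) = 0.303, so look 1 is 0.580. Look 2 is 0.580 + 0.118·0.194 + 0.303·0.448 = 0.738.
- Six with one event: look 1 is 1 − 0.7^3 = 0.657. Look 2 is 0.657 + 0.343·0.448 = 0.811.

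Chance of stopping by look 1 / by look 2:

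| Rate at 4 mcg/kg | 4 mcg/kg only | Three event-free at 2 mcg/kg | Six at 2 mcg/kg, one event |
|---|---|---|---|
| 10% | 22.5% / 24.2% | 11.4% / 13.0% | 27.1% / 29.9% |
| 20% | 56.4% / 63.3% | 34.5% / 43.9% | 48.8% / 59.2% |
| 30% | 80.4% / 88.2% | 58.0% / 73.8% | 65.7% / 81.1% |
| 40% | 92.9% / 97.5% | 76.7% / 91.3% | 78.4% / 93.2% |

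The last two columns condition on what happened at 2 mcg/kg. Before anyone is treated, if the rate is the same at both doses, the two ways of counting stop equally often (for example 80.4% / 88.2% at 30%).

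**The case against.** The strongest reply is that a 4 mcg/kg count was meant all along. The 9 and 17 are exactly the Simon sizes at that dose, Section 3.1 cites the rule straight after describing those patients, and Section 10.2 says Stage 1 is to give evidence on safety as well as effectiveness. The reference to the whole trial may describe what is stopped rather than who is counted. This stands as a plausible reading. It does not settle the matter, because Sections 10.2 and 10.3.1 keep the 2 mcg/kg patients in the safety evaluation and Section 10.2.1 names no dose.

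Three stronger inferences are not supported.

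- A reader might infer that dilution is established. It needs a lower event rate at 2 mcg/kg, or few events there by chance. Avelumab is 800 mg at both levels, so the irAE part of the rule may not differ by dose. The evidence on rhIL-15 in Section 1.2.10.2 is mixed: two DLTs at 4 mcg/kg with the 10-day infusion, none in ten patients at 3 to 5 mcg/kg with the 5-day infusion.
- A reader might infer that this is the only trial-level guard. The run-in rule also halts all enrolment and treatment, Section 7.3.1 provides weekly review of each patient, and Section 13.1 allows suspension for unacceptable risk. What is missing is a numerical limit beyond the run-in.
- A reader might take six patients at 2 mcg/kg with a 5% rate and obtain stopping chances of only 34% and 57% at a 30% rate for 4 mcg/kg. Six are treated only after one DLT among the first three, so that calculation overstates the loss.

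**Conclusion.** The point holds as an undefined denominator whose literal reading performs worse than a 4 mcg/kg count in most settings examined. Under that reading 3 to 6 of the first 9 places go to the lower dose, and the last 3 to 8 patients at 4 mcg/kg have no numerical rule. Under the other reading the gap is at most patients 18 and 19.

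At an assumed 30% rate, the loss by the second look is 88.2 − 81.1 = 7 to 88.2 − 73.8 = 14 percentage points. By the first look it is 80.4 − 65.7 = 15 to 80.4 − 58.0 = 22 points. These sizes rest on the assumed rate, on the two run-in paths shown, and on the triggering DLT counting as an event. The direction is not universal: at a 10% rate the six-patient path stops more often than a 4 mcg/kg-only count (30% against 24%). The uncovered patients do not depend on any of these assumptions.

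**What to change.** Reword Section 10.2.1 so that:

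- the first 9 and first 17 are patients treated at 4 mcg/kg, in order of first dose, including that dose's run-in patients;
- the limit of 4 events stays in force for any 4 mcg/kg patient after the 17th;
- events in 2 mcg/kg patients after the 28-day DLT window have a stated route, counted or formally reviewed. Otherwise the new wording would leave late irAEs in those patients outside every numerical rule;
- the thresholds stay as they are, with a short table of their stopping probabilities over a range of event rates.

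Sample size and efficacy design do not change. The cost is somewhat more stopping at a moderate event rate. At 10% with 4 mcg/kg, the chance is 24% by 17 patients and 26% by 19, against about 13% for whole-trial counting with three event-free patients at 2 mcg/kg. The 19-patient figure replaces the 8 later patients by 10: 0.225 + 0.387·(0.013 + 0.070) = 0.257.

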10.3 POPULATION FOR ANALYSES

10.3.1 Evaluable for Toxicity

All patients will be evaluable for toxicity from the time of their first treatment with rhIL-15 and avelumab.

10.3.2 Evaluable for objective response

Only those patients who have measurable disease present at baseline and have received at least one cycle of therapy with 4mcg/kg dose of rhIL-15, will be assessed on an intent to treat basis. Patients who discontinue treatment or die and are not restaged will be considered to be non-responders and included in calculating the response rate. Patients will have their response classified according to the definitions stated above, Section **6.3**. (NOTE: Patients who exhibit objective disease progression prior to the end of Cycle 1 will also be considered evaluable).

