2.4.1.2 Arms

Number	Name	Description
1	Safety Run-in	IL-15 by CIV infusion at escalating doses of 2, and 4 mcg/kg/day on days 1-5 of each 28-day cycle (max 4 cycles) with avelumab by IV infusion at a dose of 800mg on Day 8 and 22 of each cycle, to determine safety of dose (3-6 patients per dose level)
2	Dose Expansion	IL-15 by CIV infusion at 4 mcg/kg/day on days 1-5 of cycles 1-4 with avelumab at 800mg on Day 8 and 22 of each cycle (Total 17 patients) to determine efficacy of treatment

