10 STATISTICAL CONSIDERATIONS

10.1 STATISTICAL HYPOTHESES

10.1.1 Primary Endpoints

Overall Response (CR + PR) by irRECIST 1.1 criteria in patients who receive at least 1 cycle of therapy with the 4 mcg/kg dose of rhIL-15.

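### The plan gives two answers for a patient who stops in cycle 1 without documented progression: unreplaced failure, or outside the primary response set

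*Combined protocol and SAP*

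**What the plan says.** **Text that keeps early stoppers in.** Section 10.2 says "Patients discontinued from the trial will not be replaced and counted in an" intention-to-treat analysis, as evaluable failures. Section 10.3.2, second sentence, agrees: "Patients who discontinue treatment or die and are not restaged will be considered to be non-responders and included in calculating the response rate".

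**Text that can leave them out.** Section 10.1.1 defines the primary endpoint "in patients who receive at least 1 cycle of therapy with the 4 mcg/kg dose of rhIL-15". Section 10.3.2 opens with the same filter: "Only those patients who have measurable disease present at baseline and have received at least one cycle of therapy with 4mcg/kg dose of rhIL-15", and calls the result intention to treat. Its note adds back one group: "Patients who exhibit objective disease progression prior to the end of Cycle 1 will also be considered evaluable".

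**Numbers.** Section 10.2 sizes the trial on 9 and then 17 evaluable patients, and says "A maximum of 19 patients may be enrolled in the phase 2 part of this trial to compensate for inevaluable patients". Section 3.1 describes a scheme that "treats a total of minimum 9 or maximum 17 patients at the 4 mcg/kg dose level".

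**Schedule.** Section 3.2 sets a cycle at 28 days. Section 2.4.1.2 gives rhIL-15 in the expansion arm "on days 1-5 of cycles 1-4 with avelumab at 800mg on Day 8 and 22 of each cycle".

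**The concern.** The two sets of statements differ for one kind of patient: someone who starts rhIL-15 at 4 mcg/kg and stops during cycle 1 for toxicity, withdrawal or a similar reason, with no documented progression. The plan does not say how much treatment counts as having received a cycle. A patient who completes the day 1 to 5 infusion but misses one or both avelumab doses could be placed on either side.

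Two examples show what depends on this.

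- **Stage 1.** The first 9 treated patients have no response, and one of them stopped in cycle 1. Under the no-replacement rule this is 0/9 and the trial stops. Under the one-cycle filter it is 0/8, and a ninth evaluable patient is still due. A response there opens stage 2.
- **Final analysis.** The first 17 treated have 2 responses, and one stopped in cycle 1. Under the no-replacement rule this is 2/17 and the null is not rejected. Under the filter it is 2/16. If the place is refilled and the new patient responds, it becomes 3/17, a success. If it is not refilled, the plan has no boundary for 16.

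The trial is open-label and the investigator assesses response (Section 6.3.1). The choice could therefore be made after outcomes are known, and the exclusion would rest on an event after treatment began.

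**Working it through.** **1. The same patient under each statement** (starts at 4 mcg/kg, stops in cycle 1, no documented progression)

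| Place | Status |
|---|---|
| 10.2, discontinued patients | Evaluable failure, not replaced |
| 10.3.2, second sentence | Non-responder, included if not restaged |
| 10.1.1 | Outside, if one cycle was not received |
| 10.3.2, first sentence | Outside, if one cycle was not received |
| 10.3.2, note | Not added back; it covers progressors only |
| 10.2, 19 enrolled | Replaceable if inevaluable; term not defined |

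Measurable disease is an entry criterion (Section 2.1.1.3). Among eligible treated patients, the one-cycle requirement is thus the main stated route to being inevaluable.

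**2. The plan's own design.** Inputs from Section 10.2: null rate 5%, target 25%, stop at 0/9, succeed at 3 or more of 17. With X ~ Bin(9, p) and Y ~ Bin(8, p):

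R(p) = P(X=1)·P(Y≥2) + P(X=2)·P(Y≥1) + P(X≥3)

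- p = 0.05: 0.29854×0.05724 + 0.06285×0.33658 + 0.00836 = 0.0466
- p = 0.25: 0.22525×0.63292 + 0.30034×0.89989 + 0.39933 = 0.8122
- P(X=0) at p = 0.05 is 0.630, which matches the stated 63%. P(X≥1) at p = 0.25 is 0.925, against the stated 92%.

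The design reproduces.

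**3. Size of the conflict.** The documents give no early-stop rate f, so 5% and 10% are assumed. Two early stops in 19 (10.5%) is the most the spare places could absorb. Further assumptions: early stoppers do not respond; the first two are replaced and later ones count as failures; a share h of stops counts toward the Section 10.2.1 halt (2 of the first 9 or 4 of the first 17), applied here to the 4 mcg/kg patients in order of treatment. The response rate q among the other patients is:

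- Reading A, rates refer to all treated: q = p/(1−f)
- Reading B, rates refer to evaluable patients: q = p

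Without replacement and with h = 0, the chance of success is R(q(1−f)). Under B at p = 0.25 this is R(0.2375) = 0.7806 at f = 5% and R(0.225) = 0.7454 at f = 10%.

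Otherwise let G be the chance of success with e places filled, x responses, t treated, s halting events and k replacements:

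G(e,x,t,s,k) = (1−f)[q·G(e+1,x+1,t+1,s,k) + (1−q)·G(e+1,x,t+1,s,k)] + f[h·G(e′,x,t+1,s+1,k′) + (1−h)·G(e′,x,t+1,s,k′)]

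Here (e′,k′) = (e,k+1) if a replacement is available and (e+1,k) if not. G = 0 at e = 9 with x = 0, or once the halt is met. At e = 17, G = 1 if x ≥ 3 and 0 otherwise.

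Chance of success at the 25% target, with replacement v without:

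| f | Reading | h = 0 | h = 0.5 | h = 1 |
|---|---|---|---|---|
| 5% | A | 0.8391 v 0.8122 | 0.8226 v 0.7975 | 0.7790 v 0.7585 |
| 5% | B | 0.8096 v 0.7806 | 0.7937 v 0.7667 | 0.7518 v 0.7296 |
| 10% | A | 0.8568 v 0.8122 | 0.7968 v 0.7585 | 0.6563 v 0.6316 |
| 10% | B | 0.7969 v 0.7454 | 0.7417 v 0.6972 | 0.6121 v 0.5828 |

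The differences run from about 2.1 to 2.9 points at 5% and from 2.5 to 5.2 points at 10%.

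**Type I error with replacement.** Reading A: 5.2% (f = 5%) to 5.7% (f = 2/19) with h = 0, and 4.9% to 4.4% with h = 1. Reading B with h = 0: 4.6% to 4.3%. The design value is 4.7%. At f = 10% under the null, the gap between the two rules is 0.5 to 1.0 points.

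**The case against.** The best defence is that the text can be reconciled. Section 3.1 caps patients treated at 17, while the allowance of 19 caps patients enrolled. Together they suggest that the two spare places are for people who enrol and are never treated. If so, the allowance does not contradict the no-replacement rule, and no 18th patient could be treated. The second sentence of Section 10.3.2 also puts patients who discontinue without restaging in the denominator.

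Both arguments have force. A reader might infer that 19 and 17 flatly contradict each other, or that the plan permits replacement of treated patients. The documents establish neither. The reconciliation is not stated either: Section 10.2 leaves inevaluable undefined and speaks of enrolling enough to have 17 evaluable patients treated. Section 10.3.2 still opens with a restriction to patients with at least one cycle, and its note on progressors would be unnecessary if every early stopper were already included. The stage 1 example does not depend on an 18th treated patient.

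It may also be said that a cycle is defined. It is, as 28 days; only what counts as having received one is open.

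Finally, sizing a phase 2 trial on evaluable patients is a recognised choice. That is fair, but it needs one definition and one replacement rule, and Section 10.2 already states a different rule for patients who discontinue.

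**Conclusion.** The conflict is in the current text and should be fixed. It concerns only patients who stop in cycle 1 without documented progression, because cycle 1 progressors are evaluable under every statement.

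Its existence does not depend on any assumed rate. Its size does: the 2.1 to 5.2 point range holds at a 25% target rate, with 5% or 10% early stops, stoppers who do not respond, and at most two replacements. Section 10.2.1 refers to the whole trial, so applying it to the 4 mcg/kg patients alone is also an assumption.

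A reader might infer that the two-stage design is wrong or that type I error is clearly inflated. Neither follows. The design arithmetic is right, and type I error with replacement lies between 4.3% and 5.7% in the settings listed above, on either side of 4.7%.

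**What to change.** Align Sections 10.1.1, 10.2 and 10.3.2 with the rule for discontinued patients already in Section 10.2:

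- Define the primary set as all patients with measurable disease at baseline who start rhIL-15 at 4 mcg/kg, in order of treatment: the first 9, then the first 17.
- Allow no replacement once treated. Count anyone without a confirmed response as a non-responder.
- State that the 19-patient allowance covers only patients enrolled but never treated, consistent with Section 3.1.
- State that the 5% and 25% rates refer to this set.
- Keep the one-cycle set as a sensitivity analysis, and define what counts as having received one cycle.

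A separate wording change is needed for the secondary endpoints. Section 10.1.2 applies a one-cycle filter to adverse events, PFS and OS, although PFS and OS run from enrolment (Sections 6.3.11 and 6.3.12). Remove the filter for these. Section 10.3.1 is not a clean model, because it runs from first treatment with both drugs and avelumab starts on day 8. Word both sections as all patients who receive any study drug.

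The cost is a wording amendment with no extra patients, and a possibly lower reported response rate. If the rates refer to all treated patients, the design's 4.7% and 81.2% are kept. If 25% holds only in patients who do not stop early, power is about 78% at 5% early stops and 74.5% at 10%. Both statements leave the Section 10.2.1 halt aside.
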